#### **6.6.1.2.8. Cumulative Loss of Function Analysis for Primary Efficacy Endpoint**

This sensitivity analysis will use data representing cumulative failure to perform 22 items of PUL 2.0 in patients at multiple time points over 52 weeks.

##### **6.6.1.2.8.1. Estimand Strategy**

Failure to perform an item is defined as a score transition from 2 or 1 to 0 at evaluation. Only post-baseline failures will be considered in this analysis. For each treatment group, the mean of all such patients' individual curves will be constructed, reflecting the average cumulative number of failures over time. The higher the curve, the worse the study treatment effect. To quantify the group difference, we assume that the ratio of two corresponding underlying group-wise curves is constant over time, and use the Lin, Wei, Yang and Ying (LWYY) [17] analytic method, which is the same as the Anderson-Gill method with the robust variance estimate, to estimate this constant ratio. This summary measure can also be interpreted as the ratio of the intensities of occurrences of failures over time. If the assumption of constant ratio is not plausible, the resulting estimate reflects an averaged ratio between the two curves over time. The lower the ratio (Pamrevlumab over Placebo), the greater the treatment effect.

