**PUL 2.0 scale:**

- The PUL 2.0 scale, with maximum total score = 42

- High Level: Shoulder Dimension, 6 items: Max score = 12
- Mid-level: Elbow Dimension, 9 items: Max score = 17
- Distal level: Wrist and Hand Dimension, 7 items: Max score = 13

Only 1 item in each domain is allowed missing. The score of the missing item will be imputed by the mean of the non-missing items in the domain. If the total score of any domain is missing (the high-level domain only applies to subjects with Item A score  $\geq 3$ ), then the total score will be missing. The total score of PUL is the sum of the total scores of the three domains (if Item A score  $\geq 3$ ) or two domains (Mid-level and Distal level, if Item A score  $< 3$ ).

The last measurement prior to first dose of study drug from Muscle Function Tests (MFTs) at Day 1 will be used to establish baseline.

The primary efficacy endpoint will be analyzed using mITT as the primary analysis set.

The hypothesis to be tested for the primary efficacy analysis is:

**H0:** Change from Baseline in the total score of PUL at Week 52 for the pamrevlumab arm = Change from Baseline in the total score of PUL at Week 52 for the placebo group

Versus:

**H1:** Change from Baseline in the total score of PUL at Week 52 for the pamrevlumab arm  $\neq$  Change from Baseline in the total score of PUL at Week 52 for the placebo group

H0 will be tested at the two-sided alpha = 0.05 level of significance and will be rejected if the p < 0.05 from the test.

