**6.6.1.2.8.4. Analysis Variable**

Cumulative counts of failure to perform 22 items of PUL 2.0 at each protocol specified timepoint.

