**APPENDIX 3. PERFORMANCE OF THE UPPER LIMB (PUL) MODULE**

Performance of the Upper Limb Module for DMD 2.0 (PUL for DMD)				
Dominant arm (used for all tests):  Right  Left Elbow extension ROM full = 0°: Right: _____ Left: _____ e.g. 10° contracture = -10° Supination ROM: Right:  Full  ¾  ½  ¼ Left:  Full  ¾  ½  ¼				
Entry item A. – start with A to identify starting point for subsequent tests. Circle score for each item. DO NOT INCLUDE IN TOTAL SCORE				
Item	Score	Description		
A	0	No useful function of hands		
	1	Can use hands to hold pen or pick up a coin or drive a powered chair		
	2	Can raise 1 or 2 hands to mouth but cannot raise a cup with a 200g weight in it to mouth		
	3	Can raise plastic cup with 200g weight in it to mouth using 1 or 2 hands		
	4	Can raise both arms (to shoulder height with or without compensation), i.e. elbow bent or in extension		
	5	Can raise both arms simultaneously above head only by flexing the elbow (shortening circumference of the movement /using accessory muscles)		
	6	Can abduct both arms simultaneously elbows in extension in a full circle until they touch above the head.		
For item A: A score of 3, 4, 5, 6 on item A, start with item 1. A score of, 1, 2 start with item 7				
High level shoulder Dimension: Administer only if subject scored 3, 4, 5, 6 on item A				
Item	Description	0	1	2
1 Score from Entry item above	Shoulder abduction both arms above head “Raise your arms above your head out to the side – try and keep straight elbows”	Unable	Can raise both arms simultaneously above head only by flexing the elbow - with compensation	Can abduct both arms simultaneously elbows in extension in a full circle until they touch above the head

2	Raise both arms to shoulder height (elbows at shoulder height) “Raise your arms to shoulder level”	Unable	Can raise both arms to shoulder height either one at a time or with elbows flexed ( with compensation )	Can raise both elbows to shoulder height without compensation e.g. simultaneously with elbows straight
3	Shoulder flexion to shoulder height (no weights) “Reach out and touch my hand” – elbow to eye level	Unable	Able with compensation	Able without compensation

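### The loss-of-function sensitivity analysis misses shoulder items still scored above 0 when Item A falls below 3, because those items are then not tested and no rule scores them 0

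*SAP*

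**What the plan says.** **The count.** SAP 6.6.1.2.8.1 defines the event: "Failure to perform an item is defined as a score transition from 2 or 1 to 0 at evaluation". The analysis variable (6.6.1.2.8.4) is "Cumulative counts of failure to perform 22 items of PUL 2.0 at each protocol specified timepoint". The only handling rule in that analysis (6.6.1.2.8.3) censors the count when a patient discontinues.

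**The test form.** SAP Appendix 3 has the evaluator "start with A to identify starting point for subsequent tests". The starting point is then fixed: "A score of 3, 4, 5, 6 on item A, start with item 1. A score of, 1, 2 start with item 7". The shoulder block repeats the condition: "Administer only if subject scored 3, 4, 5, 6 on item A". Item 1 alone carries the note "Score from Entry item above".

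**The total score.** SAP 6.6.1 lists "High Level: Shoulder Dimension, 6 items: Max score = 12". When Item A is below 3, the total is the sum of "two domains (Mid-level and Distal level, if Item A score" is under 3). The same paragraph tolerates one missing item per domain, filled with the mean of the others, and says the shoulder domain applies only at Item A of 3 or more.

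**The population.** The mITT set (5.2.2) keeps baseline entry scores of 2 and above. Boys who start at 3 to 6 and later drop below 3 are therefore in the analysis.

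**The concern.** The event requires a recorded 0. The form stops producing scores for items 1 to 6 at the visit where Item A drops below 3. A boy can thus lose his remaining shoulder function between two evaluations, have that loss registered in the primary total, and contribute no shoulder failure to the analysis meant to measure cumulative loss.

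Randomisation does not deal with this. Boys already below 3 at baseline are a baseline feature, and they cannot fail items 1 to 6 on any reading. Crossing below 3 during follow-up is a post-randomisation outcome that treatment may affect.

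What is at stake is the meaning of the rate ratio as support for the primary result. The two analyses treat the same loss differently, and two programmers working from this text could derive different counts.

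**Working it through.** **Plan's own figures.** The SAP gives no expected count, rate or ratio for this analysis, so there is nothing to reproduce for it. The primary-endpoint power does reproduce: with difference 2.0, SD 2.9 and 46 per arm, the noncentrality is 2.0 / (2.9 × √(2/46)) = 3.31, and the two-sided t-test has 90.5% power. With 41 per arm it has 87.0%. Neither figure bears on this point.

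**Step 1. The rules side by side, for a boy whose Item A goes from 3 or more to below 3.**

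| Rule | Effect on items 1 to 6 at that visit |
|---|---|
| Appendix 3, start point and shoulder condition | Not administered, so no score (item 1 may still be read off Item A) |
| 6.6.1.2.8.1, failure definition | Needs a 0; none exists, so no failure |
| 6.6.1.2.8.3, censoring | Covers discontinuation only |
| 6.6.1, one missing item per domain | Cannot fill a whole skipped domain |
| 6.6.1, total score | Domain leaves the sum, so remaining shoulder points are lost |

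**Step 2. One boy.** Previous visit: entry 3, item 3 = 1, item 4 = 1, other shoulder items 0. Next visit: entry 2.
- Primary total: the shoulder contribution goes from 2 to nothing, a fall of 2 points on top of any change in items 7 to 22.
- Failure count, read literally: 0 shoulder failures.
- Failure count if skipped items score 0: 2 shoulder failures.

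**Step 3. Most items that can go uncounted**, from the form's wording. Item 1 needs arms above the head (entry 5 or 6). Item 2 needs arms to shoulder height (entry 4 or more).

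| Previous entry score | Items that can still be positive | Maximum uncounted |
|---|---|---|
| 3 | 3 to 6 | 4 |
| 4 | 2 to 6 | 5 |
| 5 or 6 | 1 to 6 | 6, or 5 if item 1 is still scored from Item A |

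These are ceilings. A shoulder item lost while Item A is still 3 or more is tested, scored 0 and counted.

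**Step 4. Direction.** Let C be the mean counted failures and U the mean uncounted failures per boy. The reported ratio is C(active)/C(placebo). The ratio for all losses is [C(active) + U(active)] / [C(placebo) + U(placebo)]. The reported ratio lies closer to 1 than the all-loss ratio when U(active)/U(placebo) is smaller than a counted ratio that is itself below 1. The means below are assumed; none is in the documents. Counted failures are 2.0 on placebo and 1.5 on active, so the reported ratio is 0.75.

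| U placebo | U active | All-loss ratio |
|---|---|---|
| 0.6 | 0.45 | 1.95 / 2.6 = 0.75 |
| 0.6 | 0.3 | 1.8 / 2.6 = 0.69 |
| 0.6 | 0.6 | 2.1 / 2.6 = 0.81 |
| 0.3 | 0.6 | 2.1 / 2.3 = 0.91 |

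The reported 0.75 can be right, too close to 1, or too far from 1.

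**The case against.** **The SAP is silent; it does not prescribe an under-count.** The count is defined over 22 items for the whole mITT, including entry-2 boys who are never given items 1 to 6, and the total score already gives the skipped domain no points. Coding skipped items as 0 is compatible with that text. This is fair, and if the database does so the losses are counted. But no sentence says it, and the failure definition read literally gives the other answer.

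**The hidden loss is limited.** Few boys are likely to keep all the weighted shoulder items until the visit at which they can no longer lift a 200 g cup to the mouth, so the ceilings in Step 3 will seldom be reached. A reader might infer that 6 of 22 items (27%) vanish per boy who crosses. The form does not support this as a general figure: at entry 3 the most is 4, and 6 requires a fall from entry 5 or 6 with item 1 also left unscored.

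**The direction is not established.** A reader might infer that if pamrevlumab works, more placebo boys cross and the ratio is therefore pulled toward 1. That does not follow. Take assumed true losses of 3.0 and 1.8 (ratio 0.60) and 2 uncounted items per crossing boy:
- 20% v 10% crossing: (1.8 − 0.2) / (3.0 − 0.4) = 0.62.
- 20% v 12%: (1.8 − 0.24) / 2.6 = 0.60.
- 20% v 15%: (1.8 − 0.3) / 2.6 = 0.58, away from 1, although more placebo boys still cross.

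**The consequence is small.** This is one of eight sensitivity analyses of the primary endpoint and carries no alpha. The same rule applies in both arms, and the primary total registers the loss. All of this stands and sets the severity.

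**Conclusion.** The point holds, as a minor one. Followed literally, 6.6.1.2.8 omits failures for shoulder items that were positive at a boy's last shoulder testing once his Item A falls from 3 or more to below 3: at most 4 items from entry 3, and at most 5 from entry 4 or higher if item 1 is still scored from Item A. The primary total does fall for the same boy.

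This rests on two assumptions: that skipped items are left without a score, and that the entry-score ceilings follow the form's wording. Events are under-counted on that reading. Neither the size nor the direction of any bias in the rate ratio can be stated, because the documents give no rate of crossing below 3 by arm. Nothing here affects the primary analysis or the Table 1 sequence.

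A related gap affects the exploratory High-level subscore (6.6.3.1), which uses the primary method. The SAP gives it no value when Item A is below 3. If it is left missing, the general missing-at-random assumption (5.3.5) applies to boys whose score is absent because their function declined.

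**What to change.** Before unblinding, add to 6.6.1.2.8:
- For boys with baseline Item A of 3 or more, items 1 to 6 not administered because Item A is below 3 are scored 0 at that evaluation for the failure count.
- Each item counts as failed at most once, even if Item A later recovers. Otherwise a boy moving back and forth across the threshold could log the same items repeatedly.
- Boys with baseline Item A below 3 are not at risk for items 1 to 6.

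Add the matching rule to 6.6.3.1, so that the High-level subscore is 0 after the drop and not missing.

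Restricting the count to the 16 items given to every boy (22 − 6) would also remove the inconsistency, but it would discard all shoulder losses.

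The cost is a short SAP amendment, for which SAP Section 1 already provides, and one derivation rule. No new data are needed.

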##### **6.6.1.2.8.2. Population of Interest**

Same as [Section 6.6.1.1.2](#)

**6.6.1.2.8.3. Intercurrent Event Handling Strategy**

If a patient discontinued, the cumulative failure number will be censored upon discontinuation.

**6.6.1.2.8.4. Analysis Variable**

Cumulative counts of failure to perform 22 items of PUL 2.0 at each protocol specified timepoint.

**6.6.1.2.8.5. Population Summary for Treatment Comparison**

All post-baseline visits during the double-blind period will be included in the analysis. Cumulative counts of failure to perform 22 items of PUL 2.0 at post-baseline visits will be analyzed using the LWYY analytic method to estimate the ratio between treatment arms. Rate ratio between 2 treatment arms including 95% CI and p-value will be reported. Sample SAS code is provided below.

```
PROC PHREG DATA=FINAL COVS(AGGREGATE);
  MODEL (TSTART, TSTOP) * STATUS(1) = TRT NUMBER;
  ID SUBJID;
  WHERE TSTART < TSTOP;
RUN;
```

Note: 1= censored. For more information, please refer to [SAS online help](#).

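### The sample code for the cumulative loss-of-function analysis does not match its stated estimand: it adjusts for an undefined NUMBER and can drop items lost at the same visit

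*SAP*

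**What the plan says.** SAP 6.6.1.2.8.1 defines the event item by item: "Failure to perform an item is defined as a score transition from 2 or 1 to 0 at evaluation". Individual curves are averaged within each arm, "reflecting the average cumulative number of failures over time", and the two group curves are assumed to stand in a constant ratio. SAP 6.6.1.2.8.4 gives the analysis variable as "Cumulative counts of failure to perform 22 items of PUL 2.0 at each protocol specified timepoint". SAP 6.6.1.2.8.5 says the counts will be "analyzed using the LWYY analytic method to estimate the ratio between treatment arms" and that the rate ratio, its 95% CI and a p-value will be reported. No covariate is named anywhere in 6.6.1.2.8.

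The sample code opens with "PROC PHREG DATA=FINAL COVS(AGGREGATE", fits "MODEL (TSTART, TSTOP) * STATUS(1) = TRT NUMBER" and filters with "WHERE TSTART < TSTOP". The only explanation is "Note: 1= censored. For more information, please refer to" the SAS online help. Neither document defines NUMBER, TSTART, TSTOP or the row layout of FINAL.

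SAP Appendix 2, Table 9, gives four post-baseline muscle-function visits: Weeks 16, 28, 40 and 52.

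**The concern.** Two features of the code can pull the estimate away from the quantity in the text.

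- **NUMBER.** In a recurrent-failure data set, and in a section that itself speaks of the cumulative failure number (6.6.1.2.8.3), a programmer could well code NUMBER as the running failure count. Treatment acts on that count. Conditioning on it compares patients who have already lost the same number of items, and so removes part of the effect being estimated.
- **The row filter.** An item's loss is seen only at a visit, so all items lost since the previous visit carry one date. If FINAL has one row per successive failure, the second and later losses at a visit start and stop on the same day and are dropped. The model then counts visits with any loss, at most 4 per patient, where the text counts items, up to 22.

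At stake is whether this sensitivity analysis is a fair check on the primary result or one that can hide a real effect.

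**Working it through.** **Inputs.** The plan gives no loss rate, ratio or power for this analysis, so there is no figure of its own to reproduce. From the documents: 22 items; visits at Weeks 16, 28, 40 and 52; 82 patients in the mITT set (SAP section 7), taken as 41 per arm. As a check on that size, a two-sided t-test with difference 2.0, SD 2.9 and 41 per arm has 87.0% power, which matches the 87% in SAP section 7. Assumed, because the documents are silent: 1 to 5 items lost per placebo patient per year, gamma frailty with variance v = 0.5 or 1, true ratio 0.60.

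**Step 1, one patient by hand.** He loses 3 items by Week 16, none by Week 28, 2 by Week 40 and none by Week 52: five failures. Sequential rows are (0,16], (16,16], (16,16], (16,40], (40,40], then (40,52] censored. The filter drops the three zero-length rows, leaving 2 of 5 failures.

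**Step 2, size of the deletion effect in closed form.** Let μ be the yearly mean number of losses. The mean in an interval of w weeks is m = μ·w/52, with w = 16, 12, 12, 12. The chance of at least one loss in the interval is 1 − (1 + v·m)^(−1/v), which is m/(1 + m) when v = 1. Take μ = 3 on placebo, 0.60 × 3 = 1.8 on pamrevlumab, and v = 1.

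- Placebo: m = 0.923 and 0.692. Visits with a loss = 0.480 + 3 × 0.409 = 1.707.
- Pamrevlumab: m = 0.554 and 0.415. Visits with a loss = 0.356 + 3 × 0.2935 = 1.237.
- Ratio after deletion: 1.237/1.707 = 0.72, against 0.60.
- Losses kept: (1.707 + 1.237)/(3 + 1.8) = 61%.

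Simulation of the coded model at this setting gave 0.73 with 63% kept. The same formula gives 0.538/0.837 = 0.64 at μ = 1, v = 0.5, and 1.707/2.213 = 0.77 at μ = 5, v = 1.

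**Step 3, simulation of the coded model.** True ratio 0.60. The first two columns are separate simulations; rejection rates belong to the first (41 per arm, robust variance aggregated by patient, 200 trials per setting).

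| Version of the analysis | μ = 1.5 to 5 | μ = 1 to 3 | Rejects |
|---|---|---|---|
| All losses counted, no NUMBER | 0.59–0.64 | 0.57–0.62 | 46–77% |
| Zero-length rows dropped, no NUMBER | 0.66–0.78 | 0.61–0.74 | 32–56% |
| Dropped, NUMBER = running failure number | 0.70–0.86 | 0.66–0.82 | 17–43% |
| Dropped, NUMBER = cumulative losses at row end | 0.87–0.95 | not run | 7–17% |
| Dropped, NUMBER = a baseline count | 0.66–0.78 | not run | 32–54% |
| One row per item from time 0, no NUMBER | 0.58–0.60 | not run | 47–73% |

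The filter deletes 19–48% of losses in the first simulation and 13–37% in the second. With a true ratio of 1.0, every version in the first simulation rejected in about 3–8% of trials, so there is no visible rise in false positives.

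**The case against.** The strongest reply is that the harm rests on two things the SAP does not say. NUMBER may be a baseline count, for example of items the patient could perform at entry; the table shows that this adds no harm. FINAL may have one row per item starting at time 0; then no zero-length rows arise and the ratio is recovered, although that is a clustered time-to-loss model and not the patient-level cumulative curve in the text. The code is also labelled as a sample, and the text states the outcome and method correctly. All of this stands, and it is why the conclusion is conditional.

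Three further points stand in part.

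- The filter is not the root cause. An interval from t to t belongs to no risk set, so deleting the WHERE line alone would repair nothing; the gap is the undefined layout.
- The assumed loss rates may be high. Each failure costs at least one PUL point, and the 12-month changes quoted in SAP section 7 are −0.84 for entry score 1 and −2.05 for entry score 3, with larger but unquantified declines for scores 4 to 6. The lower rates, where dilution is smallest, sit nearer these figures. They are net changes in total score, however, so they do not settle the number of items lost.
- Leaving out the baseline entry score is not an error. An unadjusted randomised comparison is valid.

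What the reply does not remove is that, with a true ratio of 0.60, the readings open to a programmer give average estimates from 0.58 to 0.95.

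**Conclusion.** The concern holds in conditional form. As written, the sample code does not match the estimand in SAP 6.6.1.2.8.1 and 6.6.1.2.8.4, and under natural readings it dilutes the ratio toward no effect. Pooling the two simulations, a true 0.60 is estimated at roughly 0.61–0.78 with the deletions alone and 0.66–0.86 with a running NUMBER as well. These sizes depend on the assumed loss rates, frailty and layout; at the low end the deletion effect is small.

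A reader might infer that the planned analysis is certainly biased, or that it adjusts the treatment effect away. The documents do not support that, because they define neither NUMBER nor FINAL. Nor do they support a threat to the trial's main conclusion: this is one of eight sensitivity analyses (6.6.1.2.1 to 6.6.1.2.8), it is outside the Table 1 testing sequence, and the primary test, alpha and sample size are untouched. It should still be corrected, because a sensitivity analysis that can mask a real effect is a poor check on the primary result.

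**What to change.** In SAP 6.6.1.2.8.5:

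1. Remove NUMBER from the MODEL statement, or replace it with a named baseline covariate. Adding the baseline entry score (ItemAgrp) is optional.
2. Define FINAL, TSTART and TSTOP: one row per patient per visit interval, carrying the number of items lost in that interval as the event count, with intervals without a loss kept as censored. Every loss is then counted and no zero-length row arises.
3. State that the count multiplies the event contribution only, and that each patient enters the risk set once. A plain FREQ or WEIGHT statement would also multiply the patient's share of the risk set. With common analysis visits, a Poisson model with visit as a factor and treatment, with variance clustered by patient, gives the same point estimate as counting events with Breslow ties.

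Spacing tied losses by a small time increment is a weaker alternative because it invents event times.

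The cost is a few lines of SAP code and no new data. SAP section 1 already allows changes after sign-off to be documented in an amendment or in the CSR; an amendment before unblinding is preferable.

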**6.6.2. Secondary Endpoint Estimands and Analyses**

The secondary endpoints during the on-study period (as defined in [Section 5.3.1.1](#)) will be analyzed in the order specified in [Table 1](#).

**6.6.2.1. Continuous Secondary Endpoints with RCM Model****6.6.2.1.1.1. Estimand Strategy**

Same as [Section 6.6.1.1.1](#)

**6.6.2.1.1.2. Population of Interest**

Same as [Section 6.6.1.1.2](#)

**6.6.2.1.1.3. Intercurrent Event Handling Strategy**

Same as [Section 6.6.1.1.3](#)

**6.6.2.1.2. Analysis Variables****6.6.2.1.2.1. Change in Percent Predicted Forced Vital Capacity (ppFVC) from baseline to Week 52, assessed by spirometry****6.6.2.1.3. Change in the total score of Mid-level of PUL from baseline to Week 52 Population Summary for Treatment Comparison**

Same as [Section 6.6.1.1.5](#).

